## 5.0 METHODOLOGY

### 5.1 Entry Criteria

#### 5.1.1 Diagnosis/Condition for Entry into the Trial

1. Relapsed and refractory acute myeloid leukemia (**Cohort 1**) – This cohort has enrolled the expected 40 patients and is now completed.
2. Newly diagnosed acute myeloid leukemia in older patients ( $\geq 65$  years) not candidates for intensive induction chemotherapy (**Cohort 2**) – This cohort is closed to new accrual as of 1/8/2020 based on risk benefit analysis information received from the FDA on 1/3/2020.

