### 8.2.2 Sample Size

The primary objective of this study is to estimate the complete response (CR/CRi) rate in each cohort. We estimated sample sizes for the 2 cohorts using a one-sample, one-sided binomial test, with Type I and Type II errors of 0.05 and 0.2, respectively. For Cohort 1, the null and expected response rates were taken to be 0.1 and 0.25, respectively. For Cohort 2, the null and expected response rates were taken to be 0.17 and 0.34, respectively. The sample sizes were calculated to be 38 (which will be rounded to 40) and 40 for Cohorts 1 and 2, respectively.

We used an efficient and flexible design based on Bayesian predictive probability (Lee and Liu, 2008). This design controls the type I and type II error rates and also allows flexible monitoring for futility and efficacy of the new treatment. Furthermore, this design also has better sampling properties than Simon's 2-stage design, i.e. probabilities of early termination for futility under the null hypothesis and for efficacy under the alternate hypothesis are higher and the expected sample size is lower than Simon's 2-stage design.

The following input parameters were assumed in our design: minimum and maximum number of patients was 10 and 40, respectively. Type I and II errors were 0.1 and 0.2, respectively. For cohort 1, the treatment effect for current standard was 0.1 (i.e., probability of CR/CRi) and expected treatment effect for the new treatment was 0.25. For cohort 2, the treatment effect for current standard was 0.17 and expected treatment effect for the new treatment was 0.34. A beta (0.25, 0.75) distribution was assumed for the prior for the expected effect of the new treatment. This is a weak prior, which has negligible effect on the stopping boundaries.

The stopping boundaries for futility are given in the tables below for cohorts 1 and 2. For example, the first row of Table 1 indicates that we would stop the trial for futility if we see 0 responses (CR/CRi) out of the first 10 patients after 6 cycles of therapy (to be evaluable for futility pts must complete at least 2 cycles of therapy); if the study was not stopped after 10 patients, the next evaluation will be done after 14 patients (2nd row). Study will be stopped for futility if we see 1 response or less for futility. If the study continues, the next evaluation happens after 21 patients (3rd row). Study will be stopped if we see 2 or fewer responses in the first 21 patients.

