Cohort 1: Interim monitoring boundaries for stopping for futility.

Patient. No.	Futility boundary (less than or equal to)
10	0
14	1
21	2
27	3
32	4
36	5
40	6

Cohort 2: Interim monitoring boundaries for stopping for futility.

Patient. No.	Futility boundary (less than or equal to)
10	0
11	1
16	2
20	3
24	4
27	5
31	6
34	7
36	8
39	9
40	10

For cohort 1, the expected sample size under the null and alternative hypotheses is 17.7 and 18.3, respectively. For cohort 2, these were 19.2 and 21.0.

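### The expected sample sizes stated under the alternative (18.3 and 21.0) need an early-efficacy stop that the plan does not print; the printed futility tables give 36.0 and 36.6

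*Combined protocol and SAP*

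**What the plan says.** Section 8.2.2 adopts a Bayesian predictive-probability design with 10 to 40 patients per cohort and a beta(0.25, 0.75) prior. The CR/CRi rates are 0.10 against 0.25 in Cohort 1 and 0.17 against 0.34 in Cohort 2. For this design, "Type I and II errors were 0.1 and 0.2, respectively".

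Efficacy monitoring is mentioned in general terms: "This design controls the type I and type II error rates and also allows flexible monitoring for futility and efficacy of the new treatment". The comparison with Simon's two-stage design claims a lower expected sample size and that "probabilities of early termination for futility under the null hypothesis and for efficacy under the alternate hypothesis are higher".

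What is then printed covers futility only: "The stopping boundaries for futility are given in the tables below for cohorts 1 and 2". The worked example is also about futility only. After the tables, the section states: "For cohort 1, the expected sample size under the null and alternative hypotheses is 17.7 and 18.3, respectively" and "For cohort 2, these were 19.2 and 21.0".

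Sections 8.2.2.1 and 8.2.2.2 add toxicity and GVHD rules, which do not use response. Section 5.11 (early trial termination) has no efficacy criterion. Section 5.1.1 says of Cohort 1, "This cohort has enrolled the expected 40 patients and is now completed", and of Cohort 2, "This cohort is closed to new accrual as of 1/8/2020 based on risk benefit analysis information received from the FDA on 1/3/2020".

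**The concern.** Under a futility-only rule, a treatment that works should usually run to the maximum of 40. Yet the stated expected size under the alternative is under half of that in Cohort 1 and just over half in Cohort 2, and barely above the figure under the null. That pattern arises only if the trial can also stop early for success.

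Two things depend on this. First, lower expected sample size and more frequent early termination for efficacy are among the reasons given for preferring this design to a two-stage one. Under the rules as printed, the probability of early termination for efficacy is zero. Second, the Type I error and power attached to the design depend on whether an efficacy stop was part of it, and a reader cannot tell from the plan.

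**Working it through.** **Inputs (section 8.2.2).**
- Rates: 0.10/0.25 (Cohort 1) and 0.17/0.34 (Cohort 2). Minimum 10, maximum 40. Prior beta(0.25, 0.75).
- Cohort 1 futility, stop if responses are at or below: 0 at 10, 1 at 14, 2 at 21, 3 at 27, 4 at 32, 5 at 36, 6 at 40.
- Cohort 2 futility: 0 at 10, 1 at 11, 2 at 16, 3 at 20, 4 at 24, 5 at 27, 6 at 31, 7 at 34, 8 at 36, 9 at 39, 10 at 40.
- Success at 40 is read from the last row of each table: at least 7 (Cohort 1) and at least 11 (Cohort 2). The plan prints no separate success criterion.

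**Step 1: expected size from the printed tables.** Follow the exact binomial distribution of responses patient by patient, remove paths that hit a boundary, and compute E[N] = Σ n × P(stop at n).

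Cohort 1 at a rate of 0.25: the probabilities of stopping at 10, 14, 21, 27, 32 and 36 are 0.0563 (= 0.75^10), 0.0594, 0.0225, 0.0150, 0.0137 and 0.0158. The probability of reaching 40 is 0.8174. Then E[N] = 0.563 + 0.832 + 0.473 + 0.405 + 0.438 + 0.569 + 32.696, which is 35.97 before rounding the probabilities.

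| | Null: stated | Null: tables | Alternative: stated | Alternative: tables | Type I error | Power |
|---|---|---|---|---|---|---|
| Cohort 1 | 17.7 | 19.11 | 18.3 | 35.97 | 0.069 | 0.801 |
| Cohort 2 | 19.2 | 20.27 | 21.0 | 36.64 | 0.054 | 0.789 |

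The null figures are within two patients of the stated ones. The alternative figures are not close: 35.97/18.3 = 1.97 and 36.64/21.0 = 1.74.

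**Step 2: could any futility-only rule give the stated figures?** Without an efficacy stop, success is declared only at n = 40, and every other path uses at least 10 patients. Hence E[N] ≥ 40 × power + 10 × (1 − power). At 80% power this is 0.8 × 40 + 0.2 × 10 = 34. At Cohort 2's exact power of 0.789 it is 31.56 + 2.11 = 33.7. Read backwards, E[N] = 18.3 would cap power at (18.3 − 10)/30 = 0.28, and 21.0 would cap it at 11/30 = 0.37. So an early-efficacy stop is necessary, whatever the look schedule.

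**Step 3: which efficacy rule would reproduce them? (inference)** Add a stop for efficacy when the beta-binomial predictive probability of success at 40 reaches a cut-off.

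| Rule | Cohort 1 null / alternative | Cohort 2 null / alternative |
|---|---|---|
| Stated | 17.7 / 18.3 | 19.2 / 21.0 |
| 0.94, every patient 10–39 | 17.51 / 17.74 | 19.00 / 20.26 |
| **0.95, every patient 10–39** | **17.702 / 18.348** | **19.164 / 20.973** |
| 0.96, every patient 10–39 | 17.85 / 18.87 | 19.21 / 21.20 |
| 0.95, printed looks only | 18.26 / 21.36 | 19.34 / 22.26 |
| Stop only when success is certain | 18.57 / 23.95 | 20.00 / 28.36 |

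Of these, only 0.95 after every patient matches all four figures to one decimal. Under it, Type I error is 0.087 and 0.073, power is 0.808 and 0.802, and the probability of an early efficacy stop under the alternative is 0.804 and 0.790. At the printed looks only, Type I error is 0.076 and 0.070 and power 0.804 and 0.799.

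**Step 4: Cohort 1 and its 40 patients.** Probability of reaching 40, if accrual waits for each look:

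| True rate | Futility only | Inferred 0.95 rule |
|---|---|---|
| 0.10 | 0.102 | 0.027 |
| 0.15 | 0.351 | 0.046 |
| 0.25 | 0.817 | 0.016 |
| 0.30 | 0.920 | 0.005 |

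The plan does not say that accrual waits, so this does not establish which rule was used.

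**The case against.** The best reply is that nothing was miscalculated. The section says that the design monitors efficacy, and all four stated figures fit a full predictive-probability design with an upper cut-off of 0.95. On that reading the defect is an omitted boundary, and the statement that expected size is about double holds only if no efficacy stop existed. This is right as to the probable source of the figures. It does not repair the plan: a general reference to efficacy monitoring is not a rule that anyone could apply or audit, and the rules that are printed do not produce the stated figures.

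A second reply is that every expected size here is idealised. It assumes that accrual waits for each look, although response is judged after up to six 28-day cycles, and it leaves out the toxicity hold. That stands, but it applies equally to the plan's own figures. The recalculated values should be labelled as design values for the response rule alone.

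A third is that little turns on it. Accrual is closed, and the primary analysis in section 8.2.3 is an estimate with an exact 95% interval that uses no expected sample size. That also stands, and it limits the point to stated operating characteristics and reporting. Nor should the Cohort 1 probabilities be read as evidence that a rule was ignored.

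Finally, section 8.2.2 also uses a Type I error of 0.05 in its fixed-sample calculation. All four Type I values for the printed tables and for the inferred rule are above that, though below the 0.10 set for the sequential design.

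**Conclusion.** The concern holds. The stated 18.3 and 21.0 do not follow from the printed rules, which give 36.0 and 36.6. The floor of about 34 shows that no futility-only rule with the planned power could produce them. The mismatch rests only on the printed tables, the stated rates and success being declared above the last futility row; the floor does not need even the tables. The 0.95 every-patient rule is an inference that no document states.

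Under the printed rules, Cohort 2 power is 0.789, slightly below the planned 0.80. No accrual decision changes now. What remains open is which Type I error belongs to the design: in Cohort 1, 0.069 with futility only or 0.087 with the inferred efficacy stop. This should be corrected, but it does not undermine the primary estimate.

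**What to change.** Establish which response rule was applied, and record it in a dated clarification or in the study report.

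(a) **If no efficacy stop operated**, including the case where one entered the design calculation but was never used: restate expected sizes as 19.1/36.0 (Cohort 1) and 20.3/36.6 (Cohort 2), labelled as values for the response rule alone. Withdraw the claims of efficacy monitoring and early termination for efficacy. Report Type I error 0.069/0.054 and power 0.801/0.789, noting that Cohort 2 falls slightly short of 0.80.

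(b) **If an efficacy stop was intended**: print its cut-off, boundaries and look schedule, with operating characteristics for that schedule. As a check only, a 0.95 cut-off after every patient from 10 to 39 implies these boundaries:
- Cohort 1: at least 4 responses at 10–12, 5 at 13–18, 6 at 19–25, 7 at 26–39.
- Cohort 2: at least 5 at 10, 6 at 11–13, 7 at 14–17, 8 at 18–21, 9 at 22–25, 10 at 26–31, 11 at 32–39.

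Type I error is then 0.087/0.073 and power 0.808/0.802.

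Under either option, state in the report which rule governed Cohort 1, which enrolled 40.

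The cost is SAP and report wording. Option (a) makes the stated expected sizes less favourable and shows Cohort 2 power as 0.789. Option (b) adds one boundary table.

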### **8.2.2.1 Early stopping guideline for toxicity**

Toxicity will be monitored after every 5 patients for each cohort. If it becomes evident that the proportion of patients being removed from the study for toxicity convincingly exceeds 20%, the study will be halted for a safety consultation. The toxicity stopping rule will hold enrollment if the posterior probability of failure being larger than 0.20 is 70% or higher. The prior for this monitoring rule is  $\text{beta}(0.5, 2)$ . This means that our prior guess at the proportion of failures is 20%, and there is 90% probability that this proportion is between 0.01% and 65.8%. The monitoring rule and operating characteristics are given below.

- Stop if 2 out of 5 patients removed from study:  $\text{Pr}(\text{Risk} > 0.2 | \text{Data}) = 0.77$
- Stop if 3 out of 10 patients removed from study:  $\text{Pr}(\text{Risk} > 0.2 | \text{Data}) = 0.715$

- Stop if 5 out of 15 patients removed from study:  $\text{Pr}(\text{Risk} > 0.2 \mid \text{Data}) = 0.852$
- Stop if 6 out of 20 patients removed from study:  $\text{Pr}(\text{Risk} > 0.2 \mid \text{Data}) = 0.823$
- Stop if 7 out of 25 patients removed from study:  $\text{Pr}(\text{Risk} > 0.2 \mid \text{Data}) = 0.8$
- Stop if 8 out of 30 patients removed from study:  $\text{Pr}(\text{Risk} > 0.2 \mid \text{Data}) = 0.781$
- Stop if 9 out of 35 patients removed from study:  $\text{Pr}(\text{Risk} > 0.2 \mid \text{Data}) = 0.766$
- Stop if 10 out of 40 patients removed from study:  $\text{Pr}(\text{Risk} > 0.2 \mid \text{Data}) = 0.752$

Operating Characteristics of stopping rule for toxicity, based on 5000 simulations:

True Toxicity Rate	Probability of declaring treatment too toxic	Average sample size
5%	2.9%	34.1
10%	11.5%	31.8
15%	28.9%	27.6
20%	51.1%	22.8
25%	73.1%	17.8
30%	86.8%	14.0
35%	95.9%	10.7
40%	98.8%	8.6

### 8.2.2.2 Early Stopping for Safety

The clinical failure of acute graft versus host disease will be monitored after every 5 patients who had a prior history of alloHSCT. If it becomes evident that the proportion of acute graft versus host disease grade 2-4 is greater than 33% the study would also be held for a safety consultation.

The acute GVHD grade 2-4 stopping rule will hold enrollment if the posterior probability of failure being larger than 0.33 is 70% or higher. The prior for this monitoring rule is beta(1,2). This means that our prior guess at the proportion of failures is 33%, and there is 90% probability that this proportion is between 2.5% and 77.6%. The monitoring rule and operating characteristics are given below.

- Stop if 3 out of 5 patients with gr2-4 aGVHD:  $\text{Pr}(\text{Risk} > 0.33 \mid \text{Data}) = 0.832$
- Stop if 5 out of 10 patients with gr2-4 aGVHD:  $\text{Pr}(\text{Risk} > 0.33 \mid \text{Data}) = 0.829$
- Stop if 7 out of 15 patients with gr2-4 aGVHD:  $\text{Pr}(\text{Risk} > 0.33 \mid \text{Data}) = 0.836$
- Stop if 8 out of 20 patients with gr2-4 aGVHD:  $\text{Pr}(\text{Risk} > 0.33 \mid \text{Data}) = 0.719$
- Stop if 10 out of 25 patients with gr2-4 aGVHD:  $\text{Pr}(\text{Risk} > 0.33 \mid \text{Data}) = 0.746$
- Stop if 12 out of 30 patients with gr2-4 aGVHD:  $\text{Pr}(\text{Risk} > 0.33 \mid \text{Data}) = 0.77$
- Stop if 14 out of 35 patients with gr2-4 aGVHD:  $\text{Pr}(\text{Risk} > 0.33 \mid \text{Data}) = 0.79$
- Stop if 15 out of 40 patients with gr2-4 aGVHD:  $\text{Pr}(\text{Risk} > 0.33 \mid \text{Data}) = 0.709$
- Stop if 17 out of 45 patients with gr2-4 aGVHD:  $\text{Pr}(\text{Risk} > 0.33 \mid \text{Data}) = 0.735$

True acute GVHD grade 2-4 rate	Probability of stopping for excess GVHD grade 2-4	Average Sample Size
10%	1.0%	39.7
15%	3.2%	39.0
20%	9.2%	37.3
25%	22.3%	33.9
30%	40.7%	29.4
35%	62.7%	24.2
40%	80.8%	19.1
45%	92.7%	14.5

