##### Cohort #1

1. Have histologically or cytologically confirmed relapsed or refractory AML (i.e.  $\geq 5\%$  blasts by manual differential on bone marrow aspirate/biopsy/flow cytometry), excluding acute promyelocytic leukemia (APL; FAB M3; t(15;17)).
2. Be willing and able to provide written informed consent/assent for the trial.
3. Be  $\geq 18$  years of age on day of signing informed consent.
4. Not be appropriate candidate for intensive salvage chemotherapy due to co-morbidities or other disease- or treatment-related factors.

NOTE: Subjects who received prior treatment with hypomethylating agents either for Myelodysplastic Syndrome (MDS), Myeloproliferative Neoplasm (MPN), or AML will be eligible.

NOTE: Subjects who had prior allogeneic stem cell transplant (alloHSCT) will be eligible as long as they have been at least 3 months after allogeneic HSCT and are off of all immune suppression for at least 3 weeks ( $>21$  days) and have no evidence of active graft versus

host disease (GVHD). Subjects with prior alloHSCT will NOT be eligible for enrollment during the safety run in phase.

5. Demonstrate adequate organ function as defined in Table 1, all screening labs should be performed within 14 days of treatment initiation.
6. ECOG performance status < 2.
7. A projected life expectancy of at least 12 weeks.
8. Female subject of childbearing potential should have a negative urine or serum pregnancy within 72 hours prior to receiving the first dose of study medication. If the urine test is positive or cannot be confirmed as negative, a serum pregnancy test will be required.
9. Female subjects of childbearing potential (Section 5.8.2) must be willing to use an adequate method of contraception as outlined in Section 5.8.2 – Contraception, for the course of the study through 120 days after the last dose of study medication.

Note: Abstinence is acceptable if this is the usual lifestyle and preferred contraception for the subject.

10. Male subjects of childbearing potential (Section 5.8.2) must agree to use an adequate method of contraception as outlined in Section 5.8.2- Contraception, starting with the first dose of study therapy through 120 days after the last dose of study therapy.

Note: Abstinence is acceptable if this is the usual lifestyle and preferred contraception for the subject.

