## Cohort #2

1. Have histologically and cytologically confirmed newly diagnosed AML (i.e.  $\geq 20\%$  blasts by manual differential on bone marrow aspirate/biopsy and/or in peripheral blood), excluding acute promyelocytic leukemia (APL; FAB M3, t (15;17)).
2. Be willing and able to provide written informed consent/assent for the trial.
3. Be  $\geq 65$  years of age on day of signing informed consent.
4. Have received NO prior treatment for AML with the exception of hydroxyurea/leukapheresis.

NOTE: Subjects may have been treated for pre-existent myeloid disorder such as Myelodysplastic Syndrome or Myeloproliferative Neoplasm including hypomethylating agents.

5. Demonstrate adequate organ function as defined in Table 1, all screening labs should be performed within 14 days of treatment initiation.
6. ECOG performance status < 2.
7. A projected life expectancy of at least 12 weeks.
8. Female subject of childbearing potential should have a negative urine or serum pregnancy within 72 hours prior to receiving the first dose of study medication. If the urine test is positive or cannot be confirmed as negative, a serum pregnancy test will be required.
9. Female subjects of childbearing potential (Section 5.8.2) must be willing to use an adequate method of contraception as outlined in Section 5.8.2 – Contraception, for the course of the study through 120 days after the last dose of study medication.

Note: Abstinence is acceptable if this is the usual lifestyle and preferred contraception for the subject.

10. Male subjects of childbearing potential (Section 5.8.2) must agree to use an adequate method of contraception as outlined in Section 5.8.2- Contraception, starting with the first dose of study therapy through 120 days after the last dose of study therapy.

Note: Abstinence is acceptable if this is the usual lifestyle and preferred contraception for the subject.

11. As determined by the enrolling physician or protocol designee, ability of the patient to understand and comply with study procedures for the entire length of the study.

Table 1. Adequate Organ Function Laboratory Values

System	Laboratory Value
Hematological	
White blood cell (WBC) count	$\leq 30,000/\text{mcL}$ NOTE: Hydroxyurea/leukapheresis use is allowed to meet this criterion.
Renal	

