### **8.2 Statistical Analysis Plan**

#### **8.2.1 Safety Run-In**

Each cohort will be enrolled separately with distinct null hypotheses and statistical plans. Since azacitidine and pembrolizumab have not been tested previously in combination in AML patients, we plan first to start enrollment with Cohort 1 (a safety run-in phase). Recognizing that Cohort 1 may also include patients who relapsed after allogeneic hematopoietic stem cell transplant (alloHSCT) and thus may have differential sensitivity (tolerability, immune-related adverse events [IRAEs]) to this drug combination, we will start enrollment in Cohort 1 to include patients who did not have prior alloHSCT.

The primary objective of the safety run-in is to determine the safety and tolerability of AZA followed by pembrolizumab in relapsed and refractory AML using a 3+3 design. We plan to monitor for DLTs in cycles 1, 2 and 3 as some of immunological side effects associated with pembrolizumab may occur with the delay. The first three patients will be enrolled and receive planned azacitidine and pembrolizumab in cycle 1. If 0 or 1 patient of the first three patients has a DLT (dose limiting toxicity) in cycle 1, we will enroll an additional 3 patients to better assess for toxicities. If less than 2 among first 6 patients experiences DLT in the cycle 1-3, we will open enrollment in Cohort 1 for all relapsed/refractory patients including those with prior history of alloHSCT and will also start to enroll patients in Cohort 2. If  $\geq 2$  of the first 3 patients or  $\geq 2$  of 6 patients have DLTs during cycle 1, we will perform safety (detailed toxicity) review to assess for disease versus treatment-related toxicities. Given that pembrolizumab is given only once in cycle 1 (day 8), we will first dose de-escalate azacitidine as detailed in Section 2.2. However, if the safety data analysis suggests that the toxicities are more likely pembrolizumab related, an alternative approach we may take is to exclude pembrolizumab in cycle 1 and start pembrolizumab dosing in cycle 2 when AML is better controlled but maintain azacitidine dose/schedule as described in Section 2.2. If

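### The GVHD stopping-rule table assumes 40 post-transplant patients, but Cohort 1, the only cohort planned to include them, can supply at most 34, so the stated chance of stopping at 35–45% GVHD is 5.5 to 6.8 points too high

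*Combined protocol and SAP*

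**What the plan says.** Section 8.2.2.2 sets the GVHD rule: "The clinical failure of acute graft versus host disease will be monitored after every 5 patients who had a prior history of alloHSCT". Enrollment is held if, under a beta(1,2) prior, the posterior probability that the grade 2–4 acute GVHD rate exceeds 0.33 is at least 70%. Nine boundaries follow, from 3 of 5 up to the last, "Stop if 17 out of 45 patients with gr2-4 aGVHD". A table then gives the probability of stopping and the average sample size for true rates of 10 to 45%. No maximum sample size is given for it.

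The source of these patients is described elsewhere:

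- Section 1.0 sets Cohort 1 at 10 to 40 subjects, and Section 5.1.1 reports "This cohort has enrolled the expected 40 patients and is now completed".
- Section 5.1.2, Cohort #1: "Subjects with prior alloHSCT will NOT be eligible for enrollment during the safety run in phase". Section 8.2.1 agrees: "we will start enrollment in Cohort 1 to include patients who did not have prior alloHSCT". Table 3 in Section 5.2.1.3 plans 6 run-in patients.
- Section 8.2.1 puts run-in patients treated at the selected dose and schedule into the efficacy analysis, so they count among the 40.
- Cohort 2 requires no earlier AML treatment apart from hydroxyurea or leukapheresis, but adds: "Subjects may have been treated for pre-existent myeloid disorder such as Myelodysplastic Syndrome or Myeloproliferative Neoplasm including hypomethylating agents". Transplant for such a disorder is neither named nor excluded.

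The toxicity rule in Section 8.2.2.1 has the same structure. It ends at "Stop if 10 out of 40 patients removed from study" and describes its beta(0.5, 2) prior with the words "there is 90% probability that this proportion is between 0.01% and 65.8" per cent.

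**The concern.** The rule counts only post-transplant patients, yet three of the table's eight average sample sizes (39.7, 39.0 and 37.3) exceed the 34 that Cohort 1 can provide. The table does not fit the rule's own last boundary at 45 either. It therefore seems to describe a rule run on more patients than will exist.

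The table is the plan's only statement of how well the rule detects excess GVHD. If its sample size is too large, the chance of detection is overstated at true rates above the 33% limit, where detection matters.

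**Working it through.** **Inputs.** GVHD boundaries from Section 8.2.2.2: 3/5, 5/10, 7/15, 8/20, 10/25, 12/30, 14/35, 15/40, 17/45. Toxicity boundaries from Section 8.2.2.1: 2/5, 3/10, 5/15, 6/20, 7/25, 8/30, 9/35, 10/40. Looks are every 5 patients.

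**Boundaries.** With x events in n patients the GVHD posterior is beta(1+x, 2+n−x). For 3 of 5 this is beta(4, 4), with 0.832 above 0.33, as printed. All 17 printed posterior probabilities (9 GVHD, 8 toxicity) reproduce, and one event fewer falls below 0.70 at every look. The boundaries are correct.

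**Operating characteristics.** Let f(n, x) be the probability of reaching look n with x events without having stopped. Then f(n+5, x) = Σₖ f(n, x−k) · C(5,k) pᵏ(1−p)⁵⁻ᵏ, and counts at or above the boundary are removed at each look. If s(n) is the probability removed at look n:

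- P(stop) = Σ s(n)
- average N = Σ n·s(n) + (1 − P(stop)) · Nmax

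**Which maximum does the printed GVHD table use?** Largest absolute difference from the printed columns:

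| Nmax | P(stop), points | Average N |
|---|---|---|
| 45 | 1.9 | 4.9 |
| 40 | 0.7 | 0.2 |
| 35 | 4.9 | 5.0 |
| 34 | 6.8 | 6.0 |

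Only 40 fits both columns, and the remaining differences are of the size simulation error would give. A hand check agrees. At a 10% rate the table states 1.0% stopping and an average of 39.7. With a maximum of 45 the average would be at least 0.99 × 45 = 44.6, and with a maximum of 34 it could not exceed 34.

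**What Cohort 1 can supply.** 40 − 6 = 34, and only if every patient after the run-in is post-transplant. With looks every 5, the last look is at 30.

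| True rate | Stated P(stop) / avg N | Exact, max 40 | Exact, max 34 | Stated minus max 34, points |
|---|---|---|---|---|
| 10% | 1.0 / 39.7 | 1.0 / 39.7 | 1.0 / 33.7 | 0.0 |
| 15% | 3.2 / 39.0 | 3.5 / 38.9 | 3.5 / 33.1 | −0.3 |
| 20% | 9.2 / 37.3 | 9.6 / 37.1 | 9.4 / 31.7 | −0.2 |
| 25% | 22.3 / 33.9 | 21.6 / 34.0 | 20.4 / 29.3 | 1.9 |
| 30% | 40.7 / 29.4 | 40.2 / 29.6 | 36.8 / 25.9 | 3.9 |
| 35% | 62.7 / 24.2 | 62.0 / 24.4 | 56.0 / 21.8 | 6.7 |
| 40% | 80.8 / 19.1 | 80.8 / 19.1 | 74.0 / 17.7 | 6.8 |
| 45% | 92.7 / 14.5 | 92.6 / 14.7 | 87.2 / 14.1 | 5.5 |

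The chance of not stopping is 26.0% at a 40% rate (stated: 100 − 80.8 = 19.2%) and 12.8% at 45% (stated: 100 − 92.7 = 7.3%).

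**Fewer post-transplant patients.** The documents give no expected number. If it were 20, 15 or 10 (assumptions, shown only as a range), P(stop) at a 40% rate would be 66.4, 52.8 or 45.1%.

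**Toxicity table.** At a 5% rate it states 2.9% stopping and an average of 34.1. With a maximum of 40, the 97.1% of trials that never stop contribute 0.971 × 40 = 38.8 on their own, so 34.1 is impossible. Largest differences (points / average N) are 3.2 / 4.9 at a maximum of 40, 0.9 / 0.25 at 35, and 4.2 / 4.8 at 30. The table was therefore run to 35, although the rule and the cohort go to 40. Against a maximum of 40 it understates stopping by at most 3.2 points (86.8 against 90.0% at a 30% rate).

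**Toxicity prior.** The 5th and 95th percentiles of beta(0.5, 2) are 0.0011 and 0.658. The lower limit is 0.11%, not 0.01%.

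**The case against.** **Cohort 2.** The rule names no cohort, and Cohort 2 does not expressly bar a patient transplanted for earlier MDS or MPN. If Cohort 1 supplied its full 34, one such patient would open the look at 35 (57.8 / 76.2 / 89.2% at rates of 35 / 40 / 45%, gaps of 4.9 / 4.6 / 3.5 points). Six would open the look at 40 and make the printed table right. This stands as a limit: 34 is a ceiling for Cohort 1, not strictly for the trial. But no section plans such patients, and 34 is itself an extreme count for Cohort 1.

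**Spacing of looks.** Part of the gap arises because patients 31 to 34 are never assessed. An extra look at 34 (boundary 13) would give 59.5 / 77.9 / 90.3%, reducing the gaps to 3.2 / 2.9 / 2.4 points. That is true, but the plan schedules looks only every 5 patients.

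**Simulation error.** The printed figures appear to be simulated. Exact 40 against exact 34 gives gaps of 6.0 / 6.9 / 5.4 points, so noise accounts for about 0.7 points at most.

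**Practical weight.** The table is correctly computed for 40, so the fault is an undeclared sample size, not a wrong sum. Accrual is closed, the rule only triggers a hold for consultation, and the Safety Monitoring Committee has oversight in any case. This limits the consequence but does not make the table right.

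**Conclusion.** The concern holds. The GVHD table describes a rule applied to 40 post-transplant patients, and Cohort 1 cannot supply more than 34. At that ceiling the stated stopping probabilities are too high by 6.7, 6.8 and 5.5 points at true rates of 35, 40 and 45%, by 3.9 points at 30%, and by under 2 points at 25% or less. With fewer post-transplant patients the overstatement at the higher rates grows.

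This rests on three readings: post-transplant patients come from Cohort 1 only, the 6 run-in patients count within the 40, and looks occur only at multiples of 5. The boundaries are right, so no decision taken under the rule is called into question. What changes is how much reassurance the absence of a GVHD hold would give. The toxicity-table error is minor and runs the other way, and the prior's lower limit is a small slip.

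**What to change.** Recompute the GVHD table at the number of post-alloHSCT patients actually enrolled, which the sponsor knows, with the last look at the largest multiple of 5 not above that number. If an upper bound is preferred, use the maximum-34 column above. State the maximum N under the table. Keep every boundary, and mark the looks at 35, 40 and 45 as not reachable from Cohort 1.

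In Section 8.2.2.1, replace the toxicity table with one run to 40 and state that maximum:

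| True rate | P(stop) | Average N |
|---|---|---|
| 5% | 2.8% | 39.0 |
| 10% | 12.1% | 36.1 |
| 15% | 29.2% | 31.3 |
| 20% | 52.7% | 25.3 |
| 25% | 75.2% | 19.3 |
| 30% | 90.0% | 14.4 |
| 35% | 97.0% | 10.9 |
| 40% | 99.3% | 8.6 |

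Correct the prior's lower limit there to 0.1%.

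The cost is two short calculations, two replaced tables and a line under each. No posterior probability or decision rule changes. The stated GVHD sensitivity becomes less favourable.
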